Inclusion. Participants will be JVS service-seeking adults who are unemployed, score at least five on the MINI-SPIN (Connor et al., 2001), meet structured interview criteria for SocAD. Participants taking psychotropic medications will be offered participation without restriction. We will monitor medication as a potential moderator of outcomes. Participants must agree to refrain from outside psychotherapy throughout the active 4-week treatment period.

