
POWER ANALYSIS AND STATISTICAL STRATEGY Multilevel (mixed effects) longitudinal regression (MLM) (111) and multilevel structural equation modeling (MSEM) (112) will be used for analysis. Both accommodate the multilevel, nested structure of the data, with randomization at the group level (113) and individual-level outcomes assessed repeatedly over time (114). Multilevel analysis is necessary in order to appropriately accommodate shared (nonindependent) variances due to both group-level

randomization and delivery of the WCBT intervention in groups, as well as individual-level observations repeated over time.

Aim 1. Evaluate the effects of WCBT on employment (e.g., hours worked, job search behavior, job search self-efficacy) and mental health (e.g., social anxiety, generalized anxiety, depression) compared to VAU. We hypothesize that WCBT will show greater improvements than VAU in employment and mental health symptoms at 12 weeks, 26 weeks and 52 weeks post study entrance.

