We will use the same MLM approach that we used in our R34 pilot to compare individuals assigned to WCBT vs. VAU. 3-level models will incorporate repeated measures on individuals nested within the 50 6-person groups randomly assigned to WCBT or VAU. HLM software will be used (115). Individual baseline scores on each outcome variable will be incorporated as level 2 covariates to increase the precision and statistical power of tests of the randomized intervention and reduce regression to the mean artifacts (116). Observations will be centered at a post-intervention or follow-up time point to provide a straightforward WCBT vs. VAU comparison on outcome level. Persistence of intervention effects will be assessed through WCBT vs. VAU comparisons on the level 2 slopes characterizing individual outcome trajectories through 52-week follow-up; quadratic or piecewise slope terms (117) will be included if needed to reflect acceleration or slowing of change over time. Power estimates for the planned MLM analyses were conducted using Optimal Design software (118). The entire sample of 300 individuals, nested within 50 groups, with 5 assessments over time, will provide power of .8 to detect (at 2-tailed $p < .05$) an intervention effect on intercept or slope of at least $d=0.34$; power estimates range from .7 to detect $d=.30$ to .9 to detect $d=.39$. Effect sizes in the R34 pilot ranged from .46 for hours worked to 1.36 for social avoidance; this suggests that power in this larger R01 will be adequate to detect condition differences on all outcomes, including employment. These estimates assume a minimum intraclass correlation (ICC) between groups of .01, which is larger than the ICCs observed in the R34 pilot. If the ICC for the R01 is found to be substantially higher at .03, the effect size detectable with power of .8 will rise only slightly, from $d= .34$ to $d=.36$.

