Aim 2. Evaluate whether improvements in social anxiety mediate the effect of WCBT upon employment related behaviors and outcomes. We hypothesize that reductions in social anxiety will lead to more employment related behaviors and greater employment success. In addition, it is hypothesized that specific reductions in social anxiety will better explain the effects of WCBT on employment compared with general improvements in depression and generalized anxiety. Multilevel SEM will assess whether reductions in social anxiety explain WCBT effects on subsequent employment (hours worked, job search activities, job search self-efficacy). This approach provides several advantages that are essential to testing mediation in this design. First, it accounts for nesting of individuals within randomized groups (119); it allows us to focus on change by using centering to disentangle between- and within-person effects (112); it lets us specify temporal order (i.e., change in social anxiety symptoms precedes change in employment related outcomes), and it accommodates latent variables (e.g., hours worked) (119). In addition, multilevel SEM provides ways to formally compare multiple alternative mediation paths (120), which will be essential to testing our hypothesis that reduction in social anxiety will better explain WCBT effects on employment than improvements in depression and generalized anxiety. Mplus software (121) will be used for these analyses due to its flexible estimation capabilities, use of bootstrap algorithms appropriate for testing indirect effects (122), and ability to test and compare specific mediation effects (123). Simulations conducted in MPlus and ProcClin (124) indicate that power can be expected to exceed .8 to detect significance at $p < .05$ an indirect effect in which the two component standardized direct effects a' (WCBT \rightarrow SocAD) and B' (SocAD \rightarrow employment-related outcome) are .20 or above, which is larger than the minimum a' and B' effects observed in the R34 pilot.

Aim 3. Explore moderators of the effects of WCBT, including site, race/ethnicity, education, prior work experience, psychiatric medication status and comorbid depression. Moderation will be tested by adding moderating variables to the MLM regression models testing mental health and employment outcome effects (Aim 1). Because groups are nested within site (16 sites at JVSD and 34 at JVSLA),

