site-level effect differences will be tested as level 3 interactions with condition; assuming overall average WCBT effects on a given outcome are $d=.5$ or above, power is estimated at .8 to detect a between-site effect difference of $d=.4$ or greater. Moderation by time-invariant individual characteristics (race/ethnicity, education, pre-intervention work experience) will be incorporated as cross-level interactions with condition and with condition and time, in order to test moderation of outcome change trajectory as well as level at a specific post-intervention timepoint. Because it is possible for several moderators to vary from assessment to assessment (e.g., psychiatric medication, depression diagnosis), it may be necessary to model their effects as time-varying covariates at level 1, in cross-level interaction with condition, depending on the observed levels of variability. It is not possible to know in advance how individual-level moderating variables will be distributed across the 50 randomized groups; therefore it is difficult to estimate power to test multilevel moderation of WCBT effects, and projections are necessarily tentative (125). However, assuming that a given dichotomous moderator (e.g., comorbid depression diagnosis) is present in at least 30% of the sample and is distributed relatively evenly across the 50 groups, power should exceed .8 to detect an interaction effect (i.e., between-persons difference in WCBT effect) as small as $d=.20$. Because the JVSD site is expected to have minimal variability on race/ethnicity, we plan to test moderation by this variable only among the 36 groups at the JVSLA site. Power to detect differences in WCBT effects among 3 types of participants – Hispanic (anticipated $n=49$), African-American ($n=59$), and White ($n=110$) – is estimated at .8 for interaction effects as small as $d=.30$.

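### Aim 3 allows depression and medication measured after randomisation to act as moderators; contrasts by current depression would then not be randomised comparisons, and baseline values would avoid this at almost no cost

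*Combined protocol and SAP*

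**What the plan says.** The Combined protocol and SAP lists psychiatric medication status and comorbid depression among the Aim 3 moderators, under Power Analysis and Statistical Strategy. Aim 3 treats race/ethnicity, education and work experience before the intervention as fixed personal characteristics. Medication and depression diagnosis are set apart because they can change between visits. For these, "it may be necessary to model their effects as time-varying covariates at level 1, in cross-level interaction with condition". Whether that form is used is left to be settled once data are in, "depending on the observed levels of variability", and no threshold for the choice is given.

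The Aim 3 power statement takes depression as an example of a dichotomous moderator that "is present in at least 30% of the sample". It does not say at which visit. The Inclusion paragraph adds "We will monitor medication as a potential moderator of outcomes", again without a time.

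Depression has two other roles. Aim 1 tests WCBT on "mental health (e.g., social anxiety, generalized anxiety, depression) compared to VAU" and expects greater improvement on WCBT. Aim 2 sets depression up as a rival mediator, with the hypothesis that "reduction in social anxiety will better explain WCBT effects on employment than improvements in depression and generalized anxiety".

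Two rules come close to the point but do not settle it. In the Aim 1 model, "Individual baseline scores on each outcome variable will be incorporated as level 2 covariates"; this concerns the outcome's own baseline, not the moderator's. Aim 2 describes "using centering to disentangle between- and within-person effects"; Aim 3 says nothing about centring.

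**The concern.** A moderator analysis asks whether the randomised effect differs between kinds of people. The comparison within each kind stays randomised only if membership was fixed before allocation. Depression status at 12, 26 or 52 weeks is not fixed then, and the plan itself hypothesises that WCBT changes it. Those still depressed on WCBT are a more selected group than those depressed on VAU. If depression shares causes with hours worked or social anxiety, the arms are no longer alike within a stratum.

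The plan's reason for the time-varying form is that status varies between visits. That does not address whether some of the variation is itself an effect of treatment. At stake are the exploratory statements about who benefits, which the Research Design section regards as important for dissemination.

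**Working it through.** **The plan's own figure.** The plan gives no figure for this bias. The Aim 1 power figure, for the model that Aim 3 extends, can be checked. With 50 groups of 6 and ICC .01, the variance of d is 4[.01 + .99/6]/50 = .0140, so the SE is .118. A noncentral t with 48 df gives power .804 at d = .34 (stated: .8). The base model is therefore as understood here. The Aim 3 power figures are a separate matter, and nothing below depends on them.

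**Inputs, all assumed except the number of visits.** There are four assessments after randomisation (post-treatment, 12, 26 and 52 weeks). The true effect is .40, with no moderation by baseline depression. The correlation of baseline with follow-up score is .5. Depression prevalence in VAU is .30.

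**Model.** U and S are standard normal, T is arm, and i and t index person and visit.
- Shared cause: U_it = sqrt(1-v)·U + sqrt(v)·u_it, where v is the share that varies by visit.
- Outcome: Y_it = .4T - b·U_it + c·S + e_it, with variance 1 within arm and c² = .5 - b²(1-v).
- Current depression: D_it = 1 if .7·U_it + noise - .512·T > .524, with the left side scaled to variance 1 within arm.
- Prevalence: P(Z > .524) = .30 in VAU; P(Z > .524 + .512 = 1.036) = .15 in WCBT.
- Fit: random intercept, Y on T, D, T×D and baseline Y, with D uncentred. The effect in the depressed is the T coefficient plus the interaction. The effect in the non-depressed is the T coefficient.

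**Case 1: everyone responds alike** (8 × 200,000 simulated persons per setting; small gaps are rounding):

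| b | v | Depressed | Not depressed | Interaction |
|---|---|---|---|---|
| .5 | 0 | .367 | .378 | -.011 |
| .5 | .3 | .337 | .359 | -.021 |
| .5 | .6 | .305 | .342 | -.036 |
| .3 | 0 | .381 | .389 | -.007 |
| .3 | .3 | .363 | .378 | -.015 |
| .3 | .6 | .345 | .366 | -.020 |

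Both strata are too low and the interaction barely moves. With half the shift (.30 v .22) the effects run from .36/.37 to .39/.39. With no shift they are .40/.40 within simulation error. At N = 300 the interaction has SE about .11 to .12 (ignoring group clustering), and its test rejects in 4.8% to 6.0% of runs.

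**Case 2: the same people respond on both.** Replace T by T(1 + W), W standard normal, in both the outcome and the depression equation, so that the SD of response equals its mean. WCBT prevalence becomes P(Z > 1.036/sqrt(1 + .512²)) = P(Z > .922) = .18. The spurious interaction is now about -.13 to -.15. At v = 0 the effect in the non-depressed is .41 to .42, which leaves about .26 to .27 in the depressed (.41 - .15, .42 - .15). With response SD half the mean, the interaction is about -.05 to -.06.

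**Baseline depression as moderator.** About .40/.40 in every setting of both cases.

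**Centring (Case 1).** With person-mean centring alone the condition coefficient stays at .40. If the person mean is put back at level 2, it is .29 to .30 (b = .5) or .34 (b = .3). The result therefore depends on a choice that Aim 3 leaves open.

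**A second data model.** This uses the pilot effect of .46 for hours worked, lowers depression by .3 to .5 SD, and sets the depression-outcome correlation at .3 to .5. With a homogeneous effect, attenuation is 8% to 26%. It is zero when WCBT does not change depression. Baseline depression returns .45 to .47.

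**The case against.** The strongest defence is that this is a possibility mentioned inside an exploratory aim. The plan says the time-varying form may be needed, not that it will be used. The power statement describes moderation as a difference between persons, which suggests a person-level default. Aim 3 tests interactions, and no section promises effects by stratum. Every input that sets the size is assumed. In Case 1 the bias in the depressed stratum, at most about .10, is below its own SE at N = 300 (about .11 to .12). Person-mean centring alone leaves the condition coefficient at .40.

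Much of this stands, and it is why the point is minor. Two parts do not. The person-level reading does not say that status is taken at baseline. And the interaction is safe only if everyone responds alike. In Case 2 it is displaced by .13 to .15, somewhat more than one SE, in the very quantity that Aim 3 tests.

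A reader might also infer more than the documents support:
- That the trial's main result is biased. It is not: the primary analysis is intention-to-treat, and these moderators enter only in Aim 3.
- That the bias always shrinks the effect. Case 2 shows that the non-depressed effect can be too large.
- That medication is affected in the same way. VAU procedures include referral for medication management, but WCBT participants can also be helped to find other treatment after the four weeks. The documents hypothesise no arm difference, so no direction or size can be given.

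**Conclusion.** The point holds as a minor, cheap improvement. Aim 3 leaves open a model in which current depression, a hypothesised result of treatment, defines the groups within which the arms are compared. If WCBT lowers depression and depression shares causes with the outcome, those contrasts are not randomised comparisons.

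Size and direction rest on assumptions outside the documents. With a true effect of .40, no moderation by baseline depression, prevalence .30 v about .15 to .18 and no centring:
- homogeneous response gives stratum effects of about .30 to .39 and a spurious interaction of at most about .04 in size;
- response shared between depression and outcome gives a spurious interaction of about -.13 to -.15;
- no arm effect on depression, with a homogeneous effect, gives no bias.

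For medication only the possibility is established.

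**What to change.** In Aim 3, define the depression and medication moderators by the last value before randomisation. That is the baseline MINI and the baseline Medication Use Questionnaire, or the re-assessment described under Randomization for people who wait more than a week, where it includes these items. Enter both at level 2 as person-level moderators, and drop the rule that makes the choice depend on observed variability. Any model with current status should be supplementary, labelled descriptive and non-randomised, with its centring stated.

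The cost is a few sentences in the SAP. Table 4 already schedules both instruments at baseline, so no new data are needed. The downside is that results by current depression or current medication can no longer be presented as between-arm effects.

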If a consumer agrees to consider participating and a research associate is not present at JVS, the JVS professional will ask potential participants if they would like to fill out a contact form and have a Research Associate contact them at a later time. Contact form allows participants to provide phone number for themselves and another contact and an email address, Confidentiality will be emphasized. Research Associates will re-contact potential participants who voluntarily complete contact forms by phone and briefly describe the study. If participants contact research staff via the email provided on the contact form at any time during the study, research staff will respond via email. If the potential participant remains interested, the Research Associate will schedule an in-person meeting at JVS to obtain informed consent. Once informed consent is obtained, the participant will be offered an appointment for a baseline assessment interview. After completion of the baseline assessment interview, those who qualify to participate will be offered participation. .

Participants will be 300 men and women aged 18-60 who are seeking vocational services at JVS (96 JVSD; 204 JVSLA) who meet the inclusion and exclusion criteria below. We expect to be able to recruit enough JVS consumers to fill the groups within 3 to 4 weeks depending on potential participant flow. Our screening efforts have found that approximately 27% of JVS consumers score 5 or greater on the MINI-SPIN. Of those who

score 5 or more, we anticipate that approximately 70% will agree to undergo a formal baseline interview for the pilot study. Of these, we anticipate that approximately 83% will meet full study criteria. Of these, we anticipate that 75% will be randomized. We estimate that we will need to screen 2500 people over our 34-month recruitment interval (JVSD=850; JVSLA= 1650) in order to complete the RCT. Given the large number of new clients entering JVSD and JVSLA services each year, we do not anticipate any difficulty recruiting a *minimum* of 8 participants per month at JVSLA or 6 participants per month at JVSD, but we *expect* to recruit approximately 16 per month at JVSLA and 10 per month at JVSD, resulting in an average of 15 days waiting period or less before randomization.

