Participants will be unemployed male and female adults aged 18 to 60 years, evaluated and diagnosed with social anxiety disorder (SocAD). This research is focused specifically on adults in order to determine whether adding WCBT to usual vocational services will yield superior outcomes (social anxiety symptoms and increased employment) compared to vocational services as usual control condition. Participants on medication for psychiatric conditions will be accepted into the study and medications use will be monitored throughout treatment and at each follow-up point. Those who are unwilling or unable to refrain from outside psychotherapy throughout the 4-week active treatment period will be excluded in order to lessen confounding of study treatment effects with outside therapy effects. Given that the focus of this study lies in the treatment of SocAD, participants with substance use dependence within the past month; current use of opiates or freebase cocaine; chronic neurological disorder; mental retardation; schizophrenia, other psychotic symptoms and/or current bipolar I disorder with manic symptoms that would interfere with study participation; current anorexia nervosa; medical conditions contraindicating study treatment (e.g., history of severe head trauma); or prominent suicidal/homicidal ideation with imminent risk will be excluded. These exclusions also will ensure participant safety and allow them to pursue appropriate health care directed at these other conditions.

Participants who have received a prior course of CBT appropriate for social anxiety (at least 8 sessions) will be excluded since they may represent a pre-selected treatment refractory sample that would confound the investigation of the efficacy of WCBT.

Gender and Minority Inclusion. Our screening efforts yielded a sample that was 33% female and 86% African American, 10% White, and 3% Other at JVSD. At JVSLA, administrative data suggests that we will recruit approximately 49% female participants with 35% White, 29% African American, 24% Hispanic, 10% Asian, and 1% Other. Therefore we expect that the overall sample will be mostly made up of minority group members and that men will outnumber women. All eligible and willing men and women will be enrolled regardless of minority status.

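### Aim 3's claimed power above .8 for a moderator interaction of d=.20 contradicts Aim 1's detectable main effect of d=.34; on the Aim 1 basis that power is about .12

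*Combined protocol and SAP*

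**What the plan says.** All the power statements are in Power Analysis and Statistical Strategy.

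- **Aim 1.** 300 individuals in 50 groups with 5 assessments give power .8, two-sided .05, for "an intervention effect on intercept or slope of at least $d=0.34". Power is .7 at d=.30 and .9 at d=.39. The group ICC is taken as .01; at .03 the detectable effect becomes .36.
- **Aim 3, model.** Moderators are added to the Aim 1 regression models.
- **Aim 3, individual-level moderator.** With at least 30% prevalence and a fairly even spread over the groups, "power should exceed .8 to detect an interaction effect (i.e., between-persons difference in WCBT effect) as small as $d=.20". Projections of this kind are described as tentative.
- **Aim 3, site.** Assuming an average effect of at least d=.5, "power is estimated at .8 to detect a between-site effect difference of $d=.4$ or greater".
- **Aim 3, race/ethnicity.** Moderation is tested "only among the 36 groups at the JVSLA site". Power with 49 Hispanic, 59 African-American and 110 White participants "is estimated at .8 for interaction effects as small as $d=.30".

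Three other places supply the counts. Aim 3 itself gives "16 sites at JVSD and 34 at JVSLA" (the word sites there evidently means groups). Participants and Recruitment gives "96 JVSD; 204 JVSLA". Gender and Minority Inclusion expects JVSLA to enrol "35% White, 29% African American, 24% Hispanic, 10% Asian, and 1% Other".

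**The concern.** The plan claims more power for a smaller effect on a quantity that is harder to estimate. If the whole sample can only just detect an overall effect of .34, it cannot detect a difference of .20 between the effects in two parts of that sample with at least the same power.

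This matters for reading the results. Research Design and Methods gives weak pilot power for moderators as one reason for the trial design, and treats moderators as important for dissemination. The Aim 3 paragraph is the only statement of what the trial can resolve there. A reader who trusts it would take a null moderator result as evidence against differences of .20 to .40. On the Aim 1 basis the trial resolves differences of roughly .65 to .85.

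**Working it through.** **1. Reproduce Aim 1.** Inputs from Aim 1 and the Randomization section: 50 groups of 6, allocated 25 to 25, ICC .01, two-sided .05. For a single-occasion outcome with unit variance,

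SE = sqrt(4 × (ICC + (1 − ICC)/6) / 50) = sqrt(4 × (.01 + .165)/50) = .1183.

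With a noncentral t on 48 df, the detectable d is .300, .338 and .391 at power .7, .8 and .9 (stated: .30, .34, .39). ICC .03 gives .354 (stated .36). The plan does not print this formula; it is inferred because it returns the stated figures. On this basis even a whole-sample main effect of d=.20 has power of only .38.

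**2. Individual-level moderator, same basis.** For a between-persons moderator with prevalence p, spread evenly over groups, the group variance cancels and

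SE(interaction) = 2 × sqrt((1 − ICC) / (300 × p(1 − p))).

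| Prevalence | SE | Power at d=.20 | Detectable d at power .8 |
|---|---|---|---|
| 30% | 2 × sqrt(.99/63) = .2507 | .125 | .705 |
| 50% | 2 × sqrt(.99/75) = .2298 | .140 | .646 |

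Scaling the stated .34 directly gives .34/sqrt(.21) = .742 at 30%. A simulation of 4,000 trials (50 groups of 6, ICC .01) gave power .123 at d=.20 and .799 at d=.70 for 30% prevalence, and .140 at d=.20 for 50%.

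**3. Allow for repeated measures and baseline adjustment.** The plan states no within-person correlation or R-squared, so this step rests on an assumption: four follow-ups averaged, adjusted for baseline, with a common correlation r. Residual variance is then multiplied by f = (1 + 3r)/4 − r².

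| r | f | 30% moderator: power at d=.20 | Detectable interaction | Main-effect limit |
|---|---|---|---|---|
| .5 | .375 | .254 | .43 | .207 |
| .6 | .340 | .276 | .41 | .197 |
| .7 | .285 | .319 | .38 | .181 |

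Power .8 at d=.20 needs f = (.20/.705)² = .080, that is, removal of 92% of the outcome variance. The main-effect limit would then be .338 × sqrt(.080) = .096, not .34. No single set of assumptions gives both stated figures.

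**4. Site (16 against 34 groups).** Within one site the variance of the treatment effect is 4 × .175 divided by the number of groups, so SE = sqrt(.70/16 + .70/34) = .2536. On 46 df, power at d=.4 is .339 and the detectable difference is .726. Under the step 3 assumptions power is .71, .75 and .82. The stated figure needs f = (.4/.726)² = .304, which puts the main-effect limit at .186. In a linear model the assumed average effect of d=.5 does not affect interaction power.

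**5. Race/ethnicity (49, 59 and 110).** For a 2-df test of any difference among three effects, power is .152, .129 or .119 if only the White, African-American or Hispanic effect differs by .30, and .115 if the effects are evenly spaced. Pairwise power is .12 to .15. The smallest detectable difference is .844 (White against the other two), so the stated figure needs f = (.30/.844)² = .126. Under the step 3 assumptions power is .24 to .44.

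**6. Counts.**
- 49 + 59 + 110 = 218, which exceeds the 204 planned at JVSLA.
- The JVSLA shares give .24 × 204 = 49, .29 × 204 = 59 and .35 × 204 = 71. The first two match the stated counts; the White count of 110 does not.
- 36 groups conflicts with 34 (17 + 17 in Randomization; 34 × 6 = 204).

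**The case against.** The strongest objection is that the Aim 1 basis is inferred. It is a single-occasion calculation without baseline adjustment, while the planned model has three levels, repeated measures and baseline covariates, and the ICC .03 figure matches only approximately (.354 against .36). That stands in part: the restated values are figures on the Aim 1 basis, not the definitive power of the planned model. It does not rescue d=.20. With averaging and baseline adjustment, power is .41 at r=.8 and .65 at r=.9. It passes .8 only near r=.95, where the main-effect limit would be about .08.

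Second, the site figure is attainable under plausible correlations (.71 to .82). That stands. The remaining fault is that it rests on unstated assumptions incompatible with d=.34.

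Third, the example given for the 30% moderator, comorbid depression, is also one the plan says may be modelled as time-varying. For a moderator varying entirely within person, power would be .71 at a within-person correlation of .5 and .90 at .7. But the disputed sentence defines its effect as a between-persons difference, so that reading does not fit. If it was meant, the plan must say so.

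Fourth, a single contrast of White against the other two groups (110 against 108) does better than the 2-df test: detectable d about .76, with power at .30 of .20 on the Aim 1 basis and .44 to .55 under the assumed correlations. The plan speaks of differences among three types of participant, which fits the 2-df test. The claim of .8 fails either way.

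Finally, Aim 3 is exploratory and its projections are called tentative. That lowers the importance, but the caveat concerns how moderators will be distributed over groups, and the calculation already grants an even spread.

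**Conclusion.** The concern holds. Power above .8 for a between-persons interaction of d=.20 cannot be reconciled with a detectable main effect of d=.34 in the same sample and model. On the Aim 1 basis power is about .12 at 30% prevalence and .14 at 50%, with detectable interactions of about .70 and .65. Under assumed correlations of .5 to .7 it is still only .25 to .32 at 30% prevalence. The race/ethnicity figure is also unsupported (.12 to .15 on the Aim 1 basis), and its inputs are inconsistent whatever the method. The site figure is inconsistent with Aim 1 (.34 on that basis) but not shown to be unattainable.

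These results assume an even spread of the moderator, no attrition (as in the plan's own figures) and a moderator fixed within person. The consequence is limited to how Aim 3 results, especially null ones, are read; nothing in Aim 1 changes. It should be fixed.

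**What to change.** Take one of two routes and apply it to both aims.

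1. Restate Aim 3 on the Aim 1 basis. Detectable d at power .8 is then about .70 for a 30% between-persons moderator, .65 at 50%, .73 for site, and about .84 or more for a 2-df race/ethnicity test with the plan's subgroup sizes.
2. State the within-person correlation and R-squared assumed, and recompute Aims 1 and 3 from them. This is preferable if the repeated-measures model is the one intended.

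In either case:
- Say whether each power figure refers to a between-persons or a time-varying moderator.
- Note that the assumed average effect of d=.5 plays no part in interaction power in the linear model.
- Name the race/ethnicity test and reconcile its inputs: 218 against 204 participants, 110 against about 71 White, 36 against 34 groups.
- Report interaction estimates with 95% confidence intervals, so that a null result is not read as excluding differences the trial cannot resolve.

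The cost is wording and recalculated figures. The stated Aim 3 power becomes less favourable; no participants, visits or data are added.
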